Emergency medicine residents (PGY 1-3), emergency medicine PA fellows, and emergency medicine faculty at Baylor College of Medicine will be recruited as operators. Healthy, non-pregnant emergency medicine faculty members recruited from Baylor College of Medicine who sign a written informed consent to be the subjects of the ultrasound examination will be used as the model patients.

Exclusion Criteria:

Pregnant women, adults over age 64, individuals younger than 18, and any individuals who elect not to participate or who withdraw their consent at a later date.

F2. Procedure

The FAST exam is part of standard clinical care of the trauma patient and consists of four views of the thorax and abdomen acquired with an ultrasound transducer. These views are: subxiphoid images of the heart; right upper quadrant images of the hepato-renal recess and right paracolic gutter; left upper quadrant images of the spleen-diaphragm interface, spleno-renal recess, and left paracolic gutter; and suprapubic images of the bladder and recto-vesicular or recto-vaginal pouch. Each operator will perform two ultrasound exams each with a different type of ultrasound transducer. The performance of ultrasound exams is part of standard clinical training of emergency medicine practitioners and medical students, and is considered a procedure with minimal risk to both the operator and patient. No part of the actual ultrasound exam being performed that is described here is investigational; all parts of this exam, performed with either the phased array or curvilinear probe, are considered the current standard of care for unstable trauma patients.

Prior to the ultrasound procedure we will administer a pre-survey to each participant. This survey will assess their knowledge of the adequate views of the FAST exam, their level of experience with the use of curvilinear and phased array probes, and their general level of ultrasound experience.

Each patient will be fasted for three hours prior to the exam.

Operators randomized to group A will perform an ultrasound exam on a patient using a phased-array transducer, and operators randomized to group B will perform an exam on the other patient using a curvilinear transducer. Both exams will be a complete FAST exam and each of the four exam components will be timed. After each subject in each group completes their FAST exam, they will cross-over.

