The time to complete image acquisition of each of the four parts of the FAST exam will be collected for each subject with each transducer. The ultrasound images acquired for each transducer and each view will also be evaluated to assess them for quality of the acquired images, which will be graded as either adequate (sufficient for interpretation in a real patient) or inadequate (insufficient for interpretation in a real patient).

Section G: Sample Size/Data Analysis

G1. Sample Size

How many subjects (or specimens, or charts) will be used in this study?

Local: 40 Worldwide: 40

Please indicate why you chose the sample size proposed:

This is a convenience sample of the number of expected residents, PA fellows, and faculty that we expect to participate.

G2. Data Analysis

Provide a description of your plan for data analysis. State the types of comparisons you plan (e.g. comparison of means, comparison of proportions, regressions, analysis of variance). Which is the PRIMARY comparison/analysis? How will the analyses proposed relate to the primary purposes of your study?

Time to completion of each part of the ultrasound exam, total time to completion of the ultrasound exam, and whether or not the ultrasound exam is adequate or inadequate is the dependent variable. The independent variable is the type of ultrasound transducer (curvilinear or phased array) used for the ultrasound exam. The mean values of the time to completion will be compared in this data analysis and analyzed for significance, and whether or not the exam was adequate or inadequate will be compared (through a Fisher's exact test) to determine if there is a significant difference between the curvilinear transducer and the phased array transducer groups.

The primary comparison/analysis is the time to exam completion. The secondary comparison/analysis is

whether or not the exam was adequate. This analysis will determine if the hypothesis of the study, that there is a significant difference in time to completion and adequacy of the ultrasound exam, is supported or refuted.

Section H: Potential Risks/Discomforts

H1. Potential Risks/Discomforts

Describe and assess any potential risks/discomforts; (physical, psychological, social, legal, or other) and assess the likelihood and seriousness of such risks:

This protocol does not include exposure to ionizing radiation.

There are several risks for discomfort.

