### **Study Outcomes**

In this study, the following data will be collected:

- Baseline characteristics of each participant (demographic information, training level, prior experience with performing FAST ultrasounds if known)
- Time to completion for each FAST exam performed with a phased-array transducer and for a curvilinear transducer, from start to completion of the exam
- Technical quality of each of the four required views of the FAST exam (subxiphoid, right upper quadrant, left upper quadrant, and suprapubic view)

The primary outcome of this study is time to FAST exam completion. The secondary outcome is technical quality of the ultrasound images.

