#### **Arms of the Study**

This study has two arms being compared. The first arm is the phased-array transducer arm, which collects the above mentioned outcomes for. The second arm is the curvilinear transducer arm. Each ultrasound operator will be randomized to one of the two arms to begin with. There will be no blinding of the participants or of the study investigators. After each participants completes their FAST ultrasound, they will cross-over to the other arm of the study. Thus, each participant will perform two FAST exams, one with each type of transducer.

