## **Statistical Analysis**

For the primary outcome of time to completion of the ultrasound exam, we will report descriptive statistics for each arm. We will report any differences between these descriptive statistics for each type of transducer. If there are enough participants in each subgroup to make meaningful comparisons, we may also report subgroup descriptive statistics based on the training level of the participants.

We will perform a t-test to analyze the two arms for differences in mean time to completion of each ultrasound. Additional subgroup comparisons based on the level of training of participants may be performed.

For the secondary analysis, Fisher's exact test will be used to determine if there is a statistically significant difference between the numbers of technically adequate for interpretation ultrasound exams performed for each arm. A numeric scale for quality of the images may also be used, and if so, a t-test to analyze differences in numeric scale rating of image quality between the two arms will be used.

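### Probe-specific experience is surveyed but no analysis uses it, so the trial cannot separate a transducer effect from greater familiarity with one probe

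*Protocol*

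**What the plan says.** Protocol Section F2 has every participant complete a survey before scanning. Among other things it covers "their level of experience with the use of curvilinear and phased array probes" and, as a separate item, "their general level of ultrasound experience".

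Protocol Section G2 then names a single explanatory variable: "The independent variable is the type of ultrasound transducer (curvilinear or phased array) used for the ultrasound exam". No covariate is mentioned.

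The SAP's Study Outcomes section lists, among baseline characteristics, "prior experience with performing FAST ultrasounds if known". The split by probe is absent. Its Arms of the Study section randomises only the starting arm and adds: "Thus, each participant will perform two FAST exams, one with each type of transducer".

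For the primary outcome, the SAP's Statistical Analysis section says: "We will perform a t-test to analyze the two arms for differences in mean time to completion of each ultrasound". It does not say whether the test is paired. The adequacy outcome is handled the same way, without covariates: "For the secondary analysis, Fisher's exact test will be used to determine if there is a statistically significant difference". The nearest approach to experience is optional: "Additional subgroup comparisons based on the level of training of participants may be performed". Training level does not measure how well an operator knows one probe relative to the other.

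**The concern.** An operator who has trained mainly on one probe is likely to be faster with it. In a crossover, anything that affects both of an operator's exams equally, such as general scanning skill, cancels in the within-operator difference if the analysis is paired. The gap between the operator's experience with the two probes does not cancel, because it acts on the difference itself. Randomising which probe comes first balances order effects but leaves this gap untouched.

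All operators come from one institution, so a shared leaning is plausible, although the documents do not establish one. If it exists, a significant result could reflect local training as much as the device, and a reader at a centre with different habits could not tell which. The plan does not say which of the two questions it means to answer, and it makes no use of the one variable collected that could help.

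**Working it through.** **No figure to reproduce.** Section G1 gives 40 subjects as a convenience sample, with no alpha, power, effect size or SD. What follows is illustration, in SD units.

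**Inputs.** From the documents: n = 40, two exams per operator. Section G1 does not say whether the model patients are counted in the 40, so 38 operators (assuming two model patients) was also checked. Assumed: two-sided 5%, 80% power, r = 0.2 to 0.5, k = 0 to 1.

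**Definitions.** For each operator, y is the time difference and D the experience difference, both curvilinear minus phased array. r is the absolute correlation of y with D (more experience should shorten time, so the sign under this coding would be negative). k is the mean of D divided by its SD, in absolute value.

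**Step 1: detectable difference.** From the noncentral t, a paired test detects 0.454 SD of y at n = 40 and 0.467 SD at n = 38.

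**Step 2: offset.** The unadjusted estimate is mean(y). The equal-familiarity effect is the regression of y on D read at D = 0. They differ by slope × mean(D) = (r × SD(y)/SD(D)) × (k × SD(D)) = r × k SDs of y.

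**Step 3: how often familiarity alone gives significance.** In 20,000 simulations at n = 40 with no transducer effect at equal familiarity, the unadjusted paired t-test rejected as shown below. At k = 0 it rejected in about 5%. The analysis read at D = 0 rejected in about 5% throughout.

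**Step 4: price of the equal-familiarity estimate.** Its variance relative to the unadjusted mean is about (1 − r²)(1 + k² × n/(n − 1)). For r = 0.3, k = 1: 0.91 × (1 + 40/39) = 1.84.

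| r | k | Offset (SD of y) | Unadjusted test rejects | Variance ratio at zero gap |
|---|---|---|---|---|
| 0.2 | 0.5 | 0.10 | 9.6% | 1.21 |
| 0.3 | 0.5 | 0.15 | 15.3% | 1.14 |
| 0.5 | 0.5 | 0.25 | 33.5% | 0.94 |
| 0.2 | 1 | 0.20 | 23.6% | 1.94 |
| 0.3 | 1 | 0.30 | 46.2% | 1.84 |
| 0.5 | 1 | 0.50 | 86.9% | 1.52 |

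These rejections are not type I errors for the as-trained question. They show how often a significant difference would arise from familiarity alone.

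**Step 5: does adding the gap to the primary model gain precision?** If D is centred at its sample mean, the intercept of the regression of y on D is mean(y), the unadjusted estimate itself. Its true SD at n = 40, with SD(y) = 1, is 1/√40 = 0.158 whatever r is. In simulation at r = 0.3, 0.4 and 0.5 the model reported mean SEs of 0.150, 0.144 and 0.136. For the average effect over operators in general, type I error was about 6%, 7% and 8.5%, against about 5% for the plain paired t-test.

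**The case against.** The strongest reply is that the planned contrast fits the stated purpose. Protocol Section D asks whether speed or quality differs by transducer among the people who will use it, which can fairly be read as operators as trained. For that question the within-operator difference is unbiased, and the equal-familiarity effect is a different estimand that neither document poses. This stands. It is why the primary analysis should not adjust for the gap and why the added analysis is only supportive. It does not remove the interpretive gap: the background sections of both documents ask whether choosing one transducer over the other improves acquisition time, and readers will take the result as being about the device.

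A reader might go further and infer that omitting the gap costs precision, so that adjusting for it would add power. That is not supported. Step 5 shows that the centred estimate is unchanged. The smaller SE is valid only conditional on the experience of the operators sampled, and is too small for operators in general. A paired analysis already removes general experience. The clearer precision risk is that the SAP does not say the t-test is paired. With a within-operator correlation of 0.5 (assumed), pairing halves the variance, and the detectable difference is 0.45 SD of time against (1.960 + 0.842) × √(2/40) = 0.63 SD unpaired.

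A reader might also infer that randomisation has failed, or that these operators do favour one probe. Neither is in the documents. Only the survey can show the second.

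Finally, this is a self-described pilot with a convenience sample, and the survey's response scale is not given, so a difference of two self-ratings may be a crude covariate. Both points stand and limit how much weight the added analysis can carry.

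**Conclusion.** The concern holds as one of interpretation, not of precision or validity. Data that bear directly on the within-operator difference are collected from every operator and given no role. If operators as a group know one probe better, the estimated difference includes that familiarity. Over r = 0.2 to 0.5, the part due to familiarity runs from 0.10 to 0.25 SD of the difference at k = 0.5 and from 0.20 to 0.50 SD at k = 1. The upper end exceeds the 0.45 SD that 40 operators can detect. If there is no shared leaning (k = 0), the offset is zero.

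r, k, the 5% level and the 80% power are all assumptions. The documents supply only the sample size and the design.

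**What to change.** In the SAP:

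1. Define the primary analysis as the within-operator difference in total exam time (curvilinear minus phased array), with randomised order in the model and without the experience gap. Code order as ±½, so that the intercept is the average over the two orders. Code it by assigned starting transducer and not by group letter, because Protocol Sections F1 and F2 give group A opposite starting transducers and need to be reconciled. State that this estimates the difference for operators as trained.
2. Add experience with each probe to the baseline list. State the survey scale and how the gap is formed, and report the gap's distribution.
3. Prespecify a supportive regression of the time difference on the uncentred gap and order. Report the fitted difference and confidence interval at zero gap, labelled exploratory.

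The cost is SAP wording, one degree of freedom for order in the primary model, and one more for the gap in the supportive model. No new data are needed. Writing it down beforehand matters, since the same adjustment made later would look data-driven.

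The downside falls on item 3 only. The estimate at zero gap has about 1.5 to 1.9 times the variance when k = 1, is an extrapolation if nearly all operators favour the same probe, and depends on a self-reported scale. The report should say so beside the estimate.

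### Minor: Protocol G2 treats the hypothesis of a difference as either supported or refuted, but the planned tests cannot refute a difference and neither document plans a confidence interval for it

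*Protocol*

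**What the plan says.** The form prompt in Protocol G2 asks, among other things, "How will the analyses proposed relate to the primary purposes of your study". The answer names time to exam completion as the primary comparison and adequacy as the secondary. It closes by saying the analysis will determine whether the hypothesis, "that there is a significant difference in time to completion and adequacy of the ultrasound exam, is supported or refuted". Only these two outcomes are named.

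G1 gives the sample size as "Local: 40 Worldwide: 40" and describes it as a convenience sample. Section F1 classes the study as a pilot.

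The SAP does not repeat the G2 sentence. Its Statistical Analysis section plans the following:

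- For time, "we will report descriptive statistics for each arm" and "We will report any differences between these descriptive statistics for each type of transducer".
- Also for time, "We will perform a t-test to analyze the two arms for differences in mean time to completion of each ultrasound". Whether the test is paired is not stated.
- For adequacy, "Fisher's exact test will be used to determine if there is a statistically significant difference" between the arms.

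Under Arms of the Study, the SAP describes the crossover: "Thus, each participant will perform two FAST exams, one with each type of transducer". Neither document gives an alpha, an SD, an effect of interest, an equivalence margin, a power calculation or a confidence interval.

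**The concern.** A test of difference has two possible outcomes: evidence of a difference, or not enough evidence of one. The second is not evidence that the difference is absent. That conclusion needs an interval narrow enough to exclude differences that matter, judged against a margin. G2 names no third outcome, and the plan names no interval that would let a reader judge what a null result leaves open.

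At stake is the sentence written after a null result. Protocol Section I gives the study's benefit to society as finding out whether transducer choice affects performance or time to completion. If the G2 wording is carried into the report, a non-significant p-value could be presented as showing that the choice makes no difference, while the data remain compatible with a real one.

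**Working it through.** The plan has no calculated figure to reproduce. The figures below show the precision that 40 operators would give.

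**Inputs.** n = 40 is from G1, and two exams per operator is from the SAP. Two-sided alpha 0.05 (95% confidence) is assumed, as is that all 40 subjects are operators who complete both exams. G1 does not separate operators from model patients, so 38 is shown as well.

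**1. Half-width of the 95% interval for time**

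- Paired: t(0.975, 39)/√40 = 0.320 SD of the within-operator differences (0.329 with 38).
- Unpaired: t(0.975, 78) × √(2/40) = 0.445 SD of individual times (0.457 with 38).

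Even an observed difference of exactly zero leaves differences of this size open. The documents give no SD, so the values in seconds rest on an assumed range for the relevant SD:

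| Assumed SD | Paired (SD of differences) | Unpaired (SD of times) |
|---|---|---|
| 30 s | ±9.6 s | ±13.4 s |
| 60 s | ±19.2 s | ±26.7 s |
| 120 s | ±38.4 s | ±53.4 s |

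**2. A non-significant example: observed difference of 0.3 SD**

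- Paired (SD of differences): t = 0.3 × √40 = 1.897, p = 0.065, interval 0.300 ± 0.320 = −0.02 to 0.62 SD.
- Unpaired (SD of times): t = 0.3/√(2/40) = 1.342, p = 0.18, interval 0.300 ± 0.445 = −0.15 to 0.75 SD (unrounded −0.145 to 0.745).

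If alpha is 0.05, both results are non-significant, yet both intervals include differences about twice the observed one or more.

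**3. Whether a reader could rebuild the interval**

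An unpaired interval follows from each arm's mean, SD and n. The within-operator interval also needs the correlation ρ between an operator's two times. With equal SDs in the two arms, its half-width in individual SDs is 0.320 × √(2(1 − ρ)):

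- ρ = 0: 0.452
- ρ = 0.5: 0.320
- ρ = 0.8: 0.202

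Per-arm summaries alone therefore leave the half-width anywhere from 0.45 to 0.20 SD over this assumed range. The SD of the differences, or a paired t or p value, would resolve it. The plan commits to none of these.

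**4. Adequacy**

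These are Newcombe 95% intervals with exams treated as independent, as Fisher's test treats them, and assumed identical counts with each transducer:

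- 38/40: ±12 percentage points
- 36/40: ±14
- 32/40: ±18
- 20/40: ±21

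**5. Why test and interval need a common basis and a stated precedence**

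Take 38/40 versus 33/40 adequate. Fisher's test gives p = 0.15, and the unpaired Newcombe interval, −2 to 27 points, agrees with it. If the discordant pairs are 5 versus 0, exact McNemar gives p = 0.0625, while the paired Wald interval is 2 to 23 points and excludes zero. Near the boundary, methods can disagree even on the same paired basis, so the SAP should say which governs significance.

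**The case against.** The strongest reply is that the phrase is not an operative rule. It ends an answer on an ethics-board form, sets no alpha, and is not repeated in the SAP. The analysis wording elsewhere is neutral: it asks whether there is a significant difference. Since the stated hypothesis is itself that there is a *significant* difference, 'refuted' may mean no more than 'not significant'. This stands and is why the point is minor. It does not remove the point, because the sentence does not say that is what it means, and nothing in the SAP corrects it.

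It is also fair to say that the SAP does plan an estimate. A reader might infer from the missing interval that only p-values will be reported. That is not so: differences between the arms' descriptive statistics are promised, and nothing rules out an interval. What is missing is a commitment to a measure of precision for the difference.

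Two cautions about the remedy also stand. Labelling every null result 'inconclusive' would be as mechanical as 'refuted', since a narrow interval around zero can exclude large differences. And an interval is not a full answer here. Under Protocol F1, operators change patient together with transducer, so the within-operator difference also contains any difference between the two patients. An interval built from operators' differences does not allow for that.

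**Conclusion.** The point holds as a minor matter of interpretation and reporting. With difference tests only, no margin and a convenience sample, a null result cannot refute a difference, and no interval is planned to show what it leaves open. The size is a 95% half-width of 0.32 SD of within-operator differences (paired) or 0.45 SD of individual times (unpaired), assuming 40 operators with both exams. The values in seconds, the correlations and the adequacy counts are illustrations.

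The documents do not support three stronger readings that a reader might infer:

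- **That G2 would class p = 0.065 or p = 0.18 as refuting the hypothesis.** G2 states no alpha, so this is conditional on alpha 0.05 and on taking the word literally.
- **That a null result is likely to hide a real difference.** No SD or expected effect is given, so how often this would happen is unknown.
- **That a confidence interval alone would show which transducer effects remain possible.** The change of patient with transducer prevents that.

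**What to change.** In Protocol G2, replace 'supported or refuted' with 'supported or not supported'.

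In the SAP's Statistical Analysis section, add:

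- The within-operator mean difference in time (paired t-test) and the difference in the proportion of adequate exams will each be reported with a 95% confidence interval.
- For adequacy, test and interval will be on the same paired basis, for example exact McNemar with a paired interval.
- The planned test, at a stated alpha, governs significance. A null result will be interpreted from the interval and labelled neither refuted nor automatically inconclusive.
- The interval covers operator sampling error only, because operators change patient together with transducer (Protocol F1).

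The cost is one phrase in G2 and a few sentences in the SAP, with no extra participants or data. Endpoints and their ranking are unchanged. There are two downsides. The statement after a null result becomes less definite. The SAP must also commit to a paired analysis, which settles the type of t-test it now leaves open and, for adequacy, would replace Fisher's test with a paired one.
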